3.3 EXPLORATORY OBJECTIVES

- 1. Provide data on whether the carriage of filaggrin gene mutations (one or two) associates with treatment response (possible predictive biomarker).
- 2. Provide data on whether methotrexate polyglutamate measurement can be used as a biomarker for treatment response on methotrexate.
- 3. Examine whether baseline IgE and eosinophil levels are predictors of outcome on the different therapies.

- 4. Examine whether predominant head and neck ("exposed site") eczema at baseline is a predictor of outcome on the different therapies.
- 5. Explore patient thoughts about participating in the trial, expectations of treatment, experience in the trial, experience on specific treatments and suggestions relating to the future implementation of these therapies in practice.
- 6. To assess the utility of photographs for monitoring eczema through deep learning-based severity assessments and accrue a comprehensive collection of photographs of skin, thereby establishing a critical resource for future use by investigators to improve outcomes in eczema.

4 **OUTCOME MEASURES**

4.1 **PRIMARY OUTCOME**

Objective eczema severity using EASI²⁴ (blinded assessment at 6 months, presented as mean absolute change from baseline).

4.2 SECONDARY OUTCOMES

- 1. Eczema severity measured by:
 - a. EASI (blinded assessment)
 - i. EASI50/ EASI75/ EASI90/ EASI100/ absolute EASI ≤ 7 (months 1,3,6,9,12, presented as proportion achieving these outcomes)
 - ii. Change from baseline in EASI (months 1,3,9,12, presented as mean absolute change)
 - b. Investigator Global Assessment²⁵ (vIGA-AD, blinded assessment, months 1,3,6,9,12, proportion clear/ almost clear)
- 2. Patient reported symptoms (months 1,3,6,9,12) measured by:
 - a. Patient Orientated Eczema Measure²⁶ (POEM, mean absolute change from baseline)
 - b. 11 point peak pruritus numerical rating scale²⁷ (NRS, mean absolute change from baseline)
 - c. Overall disease control²⁸ (RECAP, mean absolute change from baseline)
 - d. Patient global assessment (PtGA (5-point scale), proportion clear/ almost clear)
- 3. Quality of life measured by:
 - a. Dermatology Life Quality Index²⁹ (DLQI, months 1,3,6,9,12, mean absolute change from baseline and proportion achieving DLQI ≤ 5)
- Depression and anxiety measured by Patient Health Questionnaire 9-item³⁰ and Generalised Anxiety Disorder 7-item³¹ (PHQ-9 and GAD-7, months 6,12, mean absolute change from baseline and proportion with score < 5)
- 5. Health economic outcomes will include (months 3,6,9,12):
 - a. Resource use questionnaire
 - b. 5-level EQ-5D^{32,33} (EQ-5D-5L, months 3,6,9,12 mean utility by study arm at each time point. Used to estimate QALYs as described in the HEAP).
- 6. Safety outcomes will include (continuous to 12 months):
 - a. AEs
 - b. AEs of special interest
- 7. Adherence and Tolerability
 - a. Visual Analog Scale (VAS)³⁴ for Medications Taken (VAS, months 3,6,9,12, mean scores)
 - b. Tolerability non validated measure Likert scale (months 3,6,9,12, mean scores and frequency distribution)

5 **PARTICIPANTS**

5.1 STUDY SETTING & RECRUITMENT

The trial will be delivered in UK dermatology secondary care settings (36 centres), utilising the delivery infrastructure of the NIHR Clinical Research Network (CRN). Where local service agreements allow, blood test and blood pressure safety visits will occur at GP practices.

Partipants will be recruited from participating secondary care centres as well as via adverts in primary care, online and with partner bodies including the National Eczema Society (NES). Study sites have been identified via the UK DCTN, NIHR CRN and previous successful dermatology trial networks. The UK DCTN (http://www.ukdctn.org) has over 1000 members with an interest in conducting independent skin research and has a strong track record of successfully delivering large national multicentre trials in skin disease including eczema (14 completed trials, 8 ongoing trials). The Network has and will continue to identify experienced recruiting centres across the whole of the UK with a strong track record of recruiting to time and target.

The geographical spread of study sites and diverse recruitment strategies should expand access to participation so that research follows patient need (including under-researched areas, following INCLUDE principles for recruitment).

5.2 PARTICIPANT IDENTIFICATION

Participants will be recruited by health care professionals in secondary care via:

- Clinics
- Databases held within hospital/ pharmacy/ research units
- Study site recruitment websites
- Primary care networks
- The BEACON trial website
- Self referral in collaboration with the NES
- NIHR Be Part of Research Volunteer Service

We will advertise the study on relevant websites (e.g. BEACON website, NES website) and social media to try to reach under-served communities. The NES, the UK patient organisation for people with eczema and their carers (2700 members), will help to publicise the trial and aid recruitment. It delivers information via its website, social media, publications and a nurse-supported Helpline and reaches hundreds of thousands of people through its wider communications, active social media communities and media engagement work.

5.3 ELIGIBILITY CRITERIA

Assessment of the below eligibility criteria must be performed by a medical doctor.

5.3.1 INCLUSION CRITERIA

- 1. Patients must be deemed to have the capacity to provide fully informed consent to participate.
- 2. Adults (18 +) with a diagnosis of atopic eczema (UK Working Party Diagnostic Criteria see Appendix 5)
- 3. Moderate to severe eczema requiring systemic therapy.
- 4. Objective measure of moderate to severe eczema based on an Investigator Global Assessment (vIGA-AD) score of ≥3 at baseline.
- 5. Willing and able to comply with scheduled visits, treatment plan, laboratory tests and other study procedures.

5.3.2 EXCLUSION CRITERIA

- 1. Active dermatologic conditions that may confound the diagnosis of atopic eczema or interfere with assessment of treatment.
- 2. Prior exposure to any of the systemic therapies being investigated in the trial or those with a similar mechanism of action to the systemic therapies being investigated in the trial (see drug specific appendices for examples of excluded drugs and further information).
- 3. Receipt of any of the following:
 - a. Phototherapy (UVB TL01, UVB, PUVA, UVA1), tanning beds, oral or parenteral traditional Chinese medicine or oral systemic immunosuppressant/ immunomodulatory agent that can help eczema (including but not limited to prednisolone, azathioprine, mycophenolate mofetil, tacrolimus, Janus kinase (JAK) inhibitor or phosphodiesterase 4 inhibitor) within 4 weeks prior to randomisation.
 - b. Biologic therapy for eczema (including but not limited to amlitelimab, rocatinlimab and nemolizumab) within 3 months prior to randomisation.
 - c. Receipt of a cell-depleting agent (e.g. rituximab, alemtuzumab, cyclophosphamide, chlorambucil) for 6 months prior to randomisation or until lymphocyte count returns to normal (whichever is longer)
- 4. Any medical condition that, in the opinion of the investigator, may compromise the safety of the participant in the trial, interfere with evaluation of the IMP, or reduce the participant's ability to participate in the trial.
- 5. Receipt of live/ live attenuated vaccine 30 days prior to the baseline visit date or expected need of live / live attenuated vaccination during the trial.
- 6. Participating in another clinical trial.
- 7. Women of child-bearing potential (WOCBP*) at risk of pregnancy during the trial (i.e. sexually active women not on effective contraception **)
- 8. Women who are pregnant or breastfeeding.

* WOCBP defined as: fertile, following menarche and until becoming post-menopausal unless permanently sterile. Permanent sterilisation methods include hysterectomy, bilateral salpingectomy and bilateral oophorectomy. A postmenopausal state is defined as no menses for 12 months without an alternative medical cause.

**Effective methods of contraception include:

- combined (oestrogen and progestogen containing) hormonal contraception associated with inhibition of ovulation:
 - oral
 - intravaginal
 - transdermal
- progestogen-only hormonal contraception:
 - oral
 - injectable
 - implantable
- o intrauterine device (IUD)
- intrauterine hormone-releasing system (IUS)
- bilateral tubal occlusion
- vasectomised partner (only considered highly effective if partner is the sole sexual partner of the WOCBP and the vasectomised partner has received medical assessment of the surgical success).
- Male or female condom with or without spermicide

- o Cap, diaphragm or sponge with spermicide
- A combination of male condom with either cap, diaphragm or sponge with spermicide (double barrier methods)

5.3.3 DRUG-SPECIFIC EXCLUSION CRITERIA

See the individual drug appendices for the additional drug-specific exclusion criteria. **Please note**, as long as a participant is eligible to take ciclosporin (control arm) and at least one of the other trial treatments they can be randomised (i.e. they can meet exclusion criteria for one or more of the other treatments and still be randomised). If they fail to respond at 6 months, a predefined treatment switch (as per protocol) may or may not be possible depending on whether they still meet exclusion criteria for the relevant switch option. If the switch is not possible, they would be withdrawn from the trial at that stage.

5.4 **INFORMED CONSENT**

Informed consent will be obtained by the Principal Investigator or delegated physician at each site, following personal explanation of the trial procedures. If a participant is physically unable to sign the consent form, verbal consent in the presence of a witness can be documented on the consent form and the participant signature should be marked with an X. The following text should be written on the form: 'Participant physically unable to sign consent but has given verbal consent in the presence of [name, relationship to clinic or participant, contact information]'. The witness should sign the witness line on the consent form and the physician should sign the consent form as normal. Participants who lack capacity to provide verbal consent are not eligible to participate.

6 DATA COLLECTION & DATA ENTRY

6.1 TRIAL VISITS

Please see Table 1, Schedule of Events (section 2 Trial Design) for the tabulated trial visits and data collection.

6.1.1 VISIT WINDOWS

The screening visit can be scheduled up to 12 weeks prior to randomisation. Main trial visits are scheduled at month 1 post-randomisation and then months 3,6,9,12, with a visit window of 7 days either side (likewise for PROM data capture). In the event that a visit falls outside the target visit window of +/- 7 days, the visit should be scheduled as soon as possible and the data should be entered into the intended visit. Subsequent visits should be scheduled as per the original visit schedule. Please ensure the month 6 visit (primary endpoint) falls within the visit window where at all possible. A timepoint is considered missed if the visit is not conducted by the start of the subsequent visit window.

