E: Week 28 Safety bloods only if switched to methotrexate at 6 months

F: Week 30 Safety bloods only if switched to methotrexate at 6 months G: Week 41 & 43 Safety bloods check for patients who switched to methotrexate and dose increased only

OBJECTIVES

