APPENDIX 1 DRUG-SPECIFIC INFORMATION: CICLOSPORIN

TRIAL PARTICIPANT FLOW AND SCHEDULE OF EVENTS: CICLOSPORIN

	CICLOSPORIN SCHEDULE OF EVENTS												
Event / form	Screening	Baseline^	Week 2 Safety Visit	Week 4 (Month 1)	Week 6 Safety Visit	Week 8 Safety Visit	Week 13 (Month 3)	Week 15 Safety Visit ^B	Week 17 Safety Visit ^B	PRIMARY OUTCOME Week 26 (Month 6)	Week 39 (Month 9)	Week 52 (Month 12) End of Study Visit	Ongoing
Informed Consent	X												
Registration Form	X												
baseline)	X	Х											
Medical History and	v												
demographics	X												
Skin photography (optional)		Х								Х			
Randomisation Form (after all		х											
Status Form				Y			Y			Y	x	x	
Physical examination*	x	x		x			X			X	x	x	
Blood pressure	X	X								~			
Urinalysis	Х												
Pregnancy test*		Х											
Eczema Area and Severity Index (EASI) BLINDED ASSESSOR		x		х			x			x	x	x	
Investigator Global Assessment (vIGA-AD) BLINDED ASSESSOR		x		x			x			x	x	x	
Patient Orientated Eczema Measure (POEM)		х		Х			х			х	Х	х	
Peak pruritus numerical		х		Х			х			х	Х	х	
Eczema control (RECAP)		х		х			х			х	x	x	
Patient global assessment (PtGA)		x		X			X			X	x	x	
Dermatology Life Quality Index (DLQI)		х		х			Х			х	х	х	
EQ-5D-5L		Х					Х			Х	Х	Х	
PHQ-9		X								X		X	
GAD-7		X					v			X	v	X	
Adherence check (VAS) &		^					^			^	^	^	
Tolerability							Х			Х	Х	X	
Participant Online Surveys		Х										Х	
Dispense medication		Х					Х			Х	Х		
Screening blood tests (+DNA for filaggrin status, optional)	x												
Safety Blood Tests (can be remote)		х	х	X	X	х	Х	х	х	х	X	x	
Sarety Blood Pressure (can			Х	Х	Х	Х	Х	Х	Х	Х	X	X	
Safety urinalvsis				Х	1		х			Х	х	X	
Study medication switch		1		-	1			1	1	v		1	
review										^			
Study medication dose increment review							Х				X		
Concomitant Medications Log		v		v	 		Y			v			X
Adverse Events Log				X			X			*		 	Y
Withdrawal Form			 		1							 	X
* Physical examination (according to	o routi	ne clini	ical ca	re) requir	ed at	scree	ening a	and ba	seline,	extent of	physical	exam du	iring
follow up as deemed appropriate by investigator													
* Women of childbearing potential only. Urine test													

A: Baseline safety bloods for all treatments, at investigator discretion based upon timing of screening bloods

B: Week 15 & 17 safety bloods and safety blood pressure check if ciclosporin dose increased at week 13

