1.4.2.3 SAFETY BLOODS

The following safety bloods will be performed at weeks 2, 4, 6, 8, 13, 26, 39 and 52. For those who dose increment on ciclosporin at month 3 additional safety bloods will be performed at weeks 15 and 17 (see schedule of events, main protocol Section 2).

HAEMATOLOGY Haemoglobin Haematocrit Total and differential leukocyte count Red blood cell count Platelet count BIOCHEMISTRY Creatinine Potassium Liver function tests (LFTs) *Lipids *Urate

*screening and at months 3, 6, 9 and 12 only

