* Physical examination (according to routine clinical care) required at screening and baseline, extent of physical exam during follow up as															

deemed appropriate by investigator

** Only for those who switched treatment to methotrexate at 6 months

+ Women of childbearing potential only. Urine test

++ Repeat pregnancy test at 6 months for patients changing treatment from dupilumab or abrocitinib to methotrexate at 6 months

A: Baseline safety bloods for all treatments, at investigator discretion based upon timing of screening bloods

B: Week 15 & 17 safety bloods if methotrexate dose increased at week 13 $\,$

C: Week 28 & 30 safety bloods if switched to methotrexate at 6 months

D: Week 41 & 43 safety bloods check for patients who switched to methotrexate and dose increased only

Please note: if IMP is switched at 6 months, the schedule of events for the second IMP must be followed for the second 6 months of the trial.

CONTENTS

1 MET	HOTREXATE-SPECIFIC INFORMATION	84
1.1	BACKGROUND	
1.1.1	1 Background and mechanism	
1.1.2	2 Rationale for use of methotrexate	
1.1.3	3 Methotrexate dose justification	
1.1.4	Rationale for 6 month switch option from methotrexate (dupilumab)	
1.2	METHOTREXATE TOXICITY AND SAFETY	
1.2.1	1 Common side effects	
1.2.2	2 Uncommon side effects	
1.2.3	3 Rare side effects	
1.2.4	4 Drug interactions	
1.2.5	5 Post-treatment contraception requirements	
1.3	SELECTION OF PARTICIPANTS	
1.3.1	Participant core inclusion and exclusion criteria	
1.3.2	2 Methotrexate-specific exclusion criteria	
1.4	TREATMENT AND MONITORING OF PARTICIPANTS	
1.4.1	1 Product information	
1.4.2	2 Auxillary medicinal product: Folic acid	
1.4.3	3 Safety visits and monitoring requirements	
1.	4.3.1 Safety visits (in addition to main trial visits)	87
1.	4.3.2 Safety bloods	87
1.	4.3.3 Urine pregnancy test	87
1.4.4	4 Methotrexate polyglutamate level (months 1,3,6)	
1.4.5	5 Managing toxicity with methotrexate	
1.4.6	5 Evaluating AE's and SAE's – assessment of expectedness	
1.5	REFERENCES	

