1.4.3.1 SAFETY VISITS (IN ADDITION TO MAIN TRIAL VISITS)

All participants randomised to methotrexate will be followed up for safety at week 2. In addition, if their dose is increased at 3 months, they will be seen at weeks 15 and 17. At month 6, all patients who are switched to methotrexate will be followed for safety at weeks 28 and 30. In addition, if their dose is increased at month 9, they will be seen again at weeks 41 and 43. In the event of dose reduction, additional safety assessments should be arranged at the discretion of the investigator.

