1.4.3.2 SAFETY BLOODS

The following safety bloods will be performed at weeks 2, 4, 13, 26, 39 and 52. For those who dose increment at month 3 additional safety bloods will be performed at weeks 15 and 17. For those who switch on to methotrexate at month 6 additional safety bloods will be performed at weeks 28 and 30. For those who increase dose at month 9, further saftey bloods will be performed at weeks 41 and 43.

HAEMATOLOGY Haemoglobin Haematocrit Total and differential leukocyte count Red blood cell count Platelet count

BIOCHEMISTRY Creatinine Potassium Liver function tests (LFTs)

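### Safety checks after a ciclosporin or methotrexate dose increase, or a switch to methotrexate, are fixed at study weeks, so a change made more than 4 weeks late falls after both

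*Protocol*

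**What the plan says.** **When the triggering visit can happen.** Section 6.1.1 of the protocol gives the main visits (months 1, 3, 6, 9 and 12) a window of 7 days either side. A visit outside the window is to be held as soon as possible and its data entered under the intended visit. The outer limit is: "A timepoint is considered missed if the visit is not conducted by the start of the subsequent visit window". Lateness does not move the calendar: "Subsequent visits should be scheduled as per the original visit schedule".

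**When the checks happen.** They are given as study weeks.
- Ciclosporin, month-3 increase: "For those who dose increment on ciclosporin at month 3 additional safety bloods will be performed at weeks 15 and 17" (Appendix 1, section 1.4.2.3). Footnote B of that appendix's schedule reads "Week 15 & 17 safety bloods and safety blood pressure check if ciclosporin dose increased at week 13".
- Methotrexate, month-3 increase: "Week 15 & 17 safety bloods if methotrexate dose increased at week 13" (Appendix 2, schedule footnote B).
- Switch to methotrexate: "At month 6, all patients who are switched to methotrexate will be followed for safety at weeks 28 and 30" (Appendix 2, section 1.4.3.1). Section 1.4.3.2 says the same of the bloods.
- Month-9 methotrexate increase after a switch: "Week 41 & 43 Safety bloods check for patients who switched to methotrexate and dose increased only" (Table 1, footnote G).
- Switch to dupilumab: one safety contact at week 30, without bloods (Appendix 3, section 1.4.2.1), and first bloods at week 39 (Appendix 3 schedule).

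**Other dose changes.** Section 7.2 permits changes outside the suggested schedule where clinically indicated. The safety-visit sections of Appendices 1 and 2 mention further assessments, at the investigator's discretion, only after a dose reduction.

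**The concern.** The checks exist because of the change in treatment, but their dates are counted from randomisation. The two agree only if the change happens on time. Where the month-3, month-6 or month-9 visit slips, the participant starts the higher dose or the new drug on the day of the late visit, while the checks stay where they were. If the delay is long enough, both dates have passed before the drug is changed.

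What is at stake is participant safety, not the treatment comparison. By its own schedule the protocol wants bloods 2 and 4 weeks after these changes. Appendix 1, section 1.2.1.1, describes renal impairment on ciclosporin as frequent and potentially serious, related to dose, reversible at first and usually responsive to a lower dose. Creatinine soon after the step from 3 to 5 mg/kg is therefore the useful measurement. A switch to methotrexate is a first exposure to that drug within the trial, and Appendix 2, section 1.2.1, lists leucopenia and thrombocytopenia among its common side effects.

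**Working it through.** **Inputs**
- Main visits at weeks 4, 13, 26, 39 and 52, window of 1 week either side (Table 1; section 6.1.1).
- Routine bloods: ciclosporin at weeks 2, 4, 6, 8, 13, 26, 39, 52 (Appendix 1, section 1.4.2.3); methotrexate at weeks 2, 4, 13, 26, 39, 52 (Appendix 2, section 1.4.3.2).
- Extra bloods after a change: weeks 15/17, 28/30 or 41/43.

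**The plan's own interval, on time.** First check: 15 − 13 = 28 − 26 = 41 − 39 = 2 weeks. Second check: 17 − 13 = 30 − 26 = 43 − 39 = 4 weeks. Next routine bloods: 26 − 13 = 39 − 26 = 52 − 39 = 13 weeks.

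**How late the triggering visit can be.** Section 6.1.1 defines windows only for main visits, so the next window opens at 26 − 1 = 25, 39 − 1 = 38 or 52 − 1 = 51. The visit can count until just under 12 weeks after its nominal date.

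**Wait for scheduled bloods after a change L weeks late.** All three triggers have the same spacing, so one rule covers them:
- L under 2: checks at 2 − L and 4 − L weeks.
- L from 2 to 4: the first check has passed; the second comes at 4 − L weeks and the next bloods at 13 − L weeks.
- L over 4: both checks have passed; the next bloods come at 13 − L weeks.

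| Change made at week | Weeks late | Wait for scheduled bloods |
|---|---|---|
| 13, 26 or 39 | 0 | 2 weeks, then 4 |
| 16, 29 or 42 | 3 | 1 week, then 10 |
| just after 17, 30 or 43 | just over 4 | about 9 weeks |
| 18, 31 or 44 | 5 | 8 weeks |
| 21, 34 or 47 | 8 | 5 weeks |
| 22, 35 or 48 | 9 | 4 weeks |
| just before 25, 38 or 51 | just under 12 | about 1 week |

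Counted in days, a change one day more than 4 weeks late waits 63 − 1 = 62 days, or 8.9 weeks. If the next main visit itself uses its 7 days, that becomes 9.9 weeks. Both checks are lost for any delay over 4 weeks, but the wait exceeds 4 weeks only for delays of about 4 to 9 weeks.

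**Blood pressure on ciclosporin.** After week 17 the next reading is at week 24 in Appendix 1, section 1.4.2.2, or week 26 in the schedule table: 24 − 17 = 7 or 26 − 17 = 9 weeks.

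**Switch to dupilumab.** Under Appendix 3 there is one contact, at 30 − 26 = 4 weeks, and bloods at 39 − 26 = 13 weeks when on time. A switch more than 4 weeks late loses the contact. Its wait for bloods is then at most 39 − 30 = 9 weeks, shorter than on time.

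**Increases outside the schedule.**
- Ciclosporin or methotrexate raised at week 26: 39 − 26 = 13 weeks to the next scheduled bloods.
- Methotrexate raised at week 4: 13 − 4 = 9 weeks.
- Ciclosporin raised at week 4: 6 − 4 = 2 and 8 − 4 = 4 weeks, so routine bloods already cover it.

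**The case against.** The best defence is that section 6.1.1 decides which timepoint late data belong to and was not written to time treatment or safety visits. It asks for late visits to be held as soon as possible, and for month 6 to be in window wherever that can be done. Section 2 presents the extra visits as following from the change and in line with routine care. The week numbers can then be read as describing the on-schedule case. A prescriber who starts methotrexate at week 31 would hardly treat bloods dated weeks 28 and 30 as done. Section 6.7 allows unscheduled tests, and Appendices 1 and 2 point to the product information and to national prescribing guidance. For changes outside the schedule, leaving monitoring to the prescriber is an ordinary pragmatic choice.

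Much of this stands. It makes real harm less likely and keeps the point minor. It does not remove the gap: none of these provisions dates a check after a late or off-schedule change, and the written dates, followed literally, drop checks that the protocol itself requires.

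A reader might infer more than the documents support:
- **That every late switch loses two checks and early bloods.** Switches to dupilumab, the route from both ciclosporin and methotrexate, have one contact and no 2-week bloods to lose. Section 2 does mention bloods at a month-7 contact for switchers, at odds with Appendix 3, but that too is a single check about 4 weeks after an on-time switch.
- **That a ciclosporin increase at month 9 is planned without checks until week 52.** The Appendix 1 schedule marks a dose-increment review at week 39, but the dupilumab and abrocitinib schedules carry the same row although neither drug has a planned increase. Section 2 mentions a month-9 increase only for participants who switched, and nobody switches to ciclosporin. The row is probably template carry-over and is not evidence here.
- **That 9 weeks is the usual wait after a late change.** It is the maximum, just after the second check.

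**Conclusion.** The point holds for ciclosporin and methotrexate dose increases and for switches to methotrexate. A change more than 4 weeks late falls after both of its dated checks, and the next scheduled bloods can be up to about 9 weeks away instead of 2. A change 2 to 4 weeks late keeps one check. A switch to dupilumab more than 4 weeks late loses only its week-30 contact. Separately, and without any late visit, an increase outside the schedule has no linked check, with a wait of 13 weeks in the week-26 example.

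This rests on two readings: that the study weeks mean what they say, and that the window rule in section 6.1.1 refers to main visits, the only visits for which it defines a window. The protocol gives no rate of late visits or off-schedule increases, so the number affected cannot be estimated; it is probably small. This is a minor change of safety wording, worth making because it is cheap. It does not touch the primary comparison.

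**What to change.** State the checks as 2 and 4 weeks after the actual date of the dose increase or of the switch to methotrexate, whether or not that date is on schedule. The places to change are:
- Appendix 1, sections 1.4.2.1 to 1.4.2.3 (bloods and blood pressure), and schedule footnote B;
- Appendix 2, sections 1.4.3.1 and 1.4.3.2, and schedule footnotes B to D;
- Table 1, footnotes D to G;
- Appendix 3, section 1.4.2.1, where the dupilumab contact becomes 4 weeks after the actual switch.

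Add that bloods taken at a scheduled visit may serve where the dates coincide.

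The cost is the wording, relabelled safety visits in the eCRF, and up to two extra blood tests (with blood pressure on ciclosporin) for participants whose change is late or off schedule. Participants who change on time have the same tests as now. The EASI visits and the analysis are unaffected.
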